#### Inclusion criteria:

- Criterion 1: subjects will be included in the study if they are within one of the following groups:
  - Known to be in normal sinus rhythm, are normotensive and have no underlying health problems.
  - Known to be in normal sinus rhythm and have controlled hypertension. This must have been diagnosed by a healthcare professional and the patient should be taking appropriate antihypertensive medication.
  - Known to have chronic atrial fibrillation (persistent or permanent AF). This must have been diagnosed by a healthcare professional and the patient should be appropriately anticoagulated.
- Criterion 2: subjects should ideally be ≥ 50 years, but subjects will be age matched across all three groups.
- Criterion 3: patients should have an EF  $\ge$  50%.
- Criterion 4: good quality TTE images.
- Criterion 5: No valvular pathologies.
  - Patients with AF that have < moderate valvular pathologies may be considered (as per the British Society of Echocardiography Guidelines).

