	Patients that are suspected of having AF are referred for an ultrasound scan of the heart (echocardiogram). It is expected to see structural changes to the heart's chambers. However, structural and electrical changes of the heart may be the cause of AF but may also be a result of AF, resulting in a chicken and egg situation. It may be possible that a different type of measurement can be used during an echocardiogram to detect subtle changes in heart muscle patterns. This measurement may then serve to be an early predictor of AF. This would be determined by comparing the patterns in patients with a normal, regular rhythm to those with AF.
	Potential candidates are initially screened based on their echocardiogram referral. If deemed suitable for this study, the study

	process is explained to the patient and written informed consent is invited and received. The echocardiogram will be performed as normal with a focus on the area and volume measurements taken of one of the top chambers of the heart. An additional measurement will be taken to observe any subtle changes in the arrangement of heart cells within this same heart chamber. These measurements can be compared to each other to establish any relationship as well as compared to patients with and without AF.
Objectives	To determine whether there is a significant difference in atrial strain values between patients that are in normal sinus rhythm (NSR, control group) to patients that are known to have atrial fibrillation (disease group). A disease-control group of controlled hypertensive patients in NSR will also be utilised as hypertension is a known risk factor for atrial fibrillation.
	Providing that there is a significant difference in the values between NSR and AF patients, a further comparison will be conducted on patients in different type of AF: paroxysmal AF, persistent AF and permanent AF to determine if there is a deterioration in atrial strain values within AF patients.
	Left atrial area and volume size will also be measured in all patients and this can then be compared to atrial strain values.
Sample Size	234
Duration	1 year – project end date of March 2024

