# **1. Introduction**

Atrial fibrillation (AF) is the most prevalent type of arrhythmia within an adult population and is characterised by disorganised, chaotic, electrical activity and thus ineffective atrial contraction causing irregular ventricular contraction (Wyndham, 2000). AF can be categorised into three different groups: paroxysmal, persistent, and permanent. The prevalence of AF increases with age and is associated with, but not limited to, a range of risk factors including hypertension, obesity, and alcohol consumption (Staerk, *et al.*, 2017). There is a plethora of both cardiac and non-cardiac causes of AF and the cause is not always clear for each patient. Furthermore, causes of AF can also present as the by-product of AF, this increases the difficulty in determining the individual patient's cause of onset. A diagnosis of AF can be incidental as not all patients are symptomatic. If AF goes undetected, this puts the patient at an increased risk of blood clot formation and stroke (Markides and Schilling, 2003).

Patients suspected of having AF are routinely referred for a transthoracic echocardiogram (TTE). It is common for AF patients to have a dilated left atrium (LA) and this can be visually confirmed in addition to the LA area and volume measurements (Van De Vegte, et al., 2021). However, as LA measurements are limited to area and volume size, LA strain measurements may be taken but these are not routinely performed during standard TTEs. LA strain is measured using a type of speckle-tracking echocardiography (STE) technique which focuses on the subtle longitudinal changes within the myocardium to analyse myocardial deformation (Gan, et al., 2018). Strain imaging of the LA produces three functional strain values (contractile, conduit and reservoir) which correspond to different stages of the cardiac cycle (Jarasunas, et al., 2018). As patients in AF lack normal atrial contraction and have a loss of atrial kick, it is expected that the contractile strain, associated with LA contraction, is not present. However, the conduit and reservoir functions can still be compared across all three study groups to create a scale to suggest and predict whether a patient is likely to develop AF in the future; prior to any changes in LA size. Furthermore, this can then be further compared to determine whether there are any significant differences in strain patterns between the different groups of AF.

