The correlation between AF and a dilated LA are widely recognised, however, LA enlargement may be both a cause and consequence of AF. Dilation of the LA has been largely suggested to be due to atrial remodelling as a result of a change in atrial function and structure – as seen in the case of AF. However, there are other factors which affect atrial function and structure which ultimately result in atrial remodelling. This includes pathologies such as mitral valve disease (mitral stenosis, regurgitation, or a mixed disease), structural cardiac disease (such as heart failure, cardiomyopathies, and congenital disease) and hypertension (Van De Vegte, *et al.*, 2021). As hypertension can also cause atrial remodelling and is a risk factor for AF, patients that are in normal sinus rhythm (NSR) that have controlled hypertension are included in this study as a disease-control group. It is expected that the atrial strain values of these patients will fall between those of the control group (NSR) and of those in the disease group (chronic AF).

Existing available literature (see document Literature Review Table) suggests that there is a significant difference in the strain values between patients in NSR to those in AF. However, limited studies have included hypertensive patients or investigated

the differences in strain values between AF patients. Furthermore, previous studies have been limited by method technique. This is because many studies have either used external STE software to create atrial strain values or have adopted global longitudinal strain (GLS) methods to track the LA. This is a significant limiting factor as GLS methods are intended to assess longitudinal function of the left ventricle.

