#### Exclusion criteria:

- Criterion 1: subjects with any valvular pathologies in the control and disease-control groups.
- Criterion 2: subjects with AF that have ≥ moderate valvular pathologies (as per the British Society of Echocardiography Guidelines).
- Criterion 3: subjects with an EF < 50%.
- Criterion 4: subjects < 50 years old.
- Criterion 5: poor quality TTE images.
- Criterion 6: inability to provide informed consent.
- Criterion 7: permanent atrial / ventricular pacing.
- Criterion 8: previous cardiac surgery.
- Criterion 9: unsatisfactory tracking of the LA endocardial border.
- Criterion 10: patients unwilling to have their results potentially published

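### The NSR–AF comparison is unadjusted although controls must be normotensive and AF participants need not be, so the difference can include a hypertension effect; the hypertensive sinus-rhythm group is only a partial safeguard

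*Combined protocol and SAP*

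**What the plan says.** Section 2.2.4 defines the sinus-rhythm controls as "Known to be in normal sinus rhythm, are normotensive and have no underlying health problems" and the disease-control group as "Known to be in normal sinus rhythm and have controlled hypertension", on treatment. AF participants need diagnosed persistent or permanent AF and appropriate anticoagulation; blood pressure is not mentioned. All three groups are to be age-matched. Ejection fraction below 50%, permanent pacing and previous cardiac surgery are excluded throughout.

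The Introduction gives the reason for the third group: "As hypertension can also cause atrial remodelling and is a risk factor for AF". It expects strain in that group to lie between the other two. It also plans to use conduit and reservoir strain "to create a scale to suggest and predict whether a patient is likely to develop AF in the future".

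Section 2.2.6 plans a t-test (or Mann-Whitney) for NSR against AF and a one-way ANOVA (or Kruskal-Wallis) across the three groups. Neither has covariates, and no AF versus hypertensive-NSR contrast is named. The one regression mentioned serves the prediction question and lists no covariates. The data items in sections 2.2.2 and 4.4 include demographics and study group. Hypertension status within AF is not named, although the list in 4.4 is open-ended.

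**The concern.** By the protocol's own account, hypertension is related both to belonging to the AF group and to the state of the atrium. Eligibility fixes its prevalence at zero in the NSR controls and leaves it free in AF. The NSR–AF difference is then the effect of AF plus whatever hypertension contributes among the hypertensive AF participants.

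Attributing the whole difference to AF would overstate the AF part. A scale built on it would partly sort patients by hypertension, although section 1.1 sets out to minimise outside influences on strain. The hypertensive sinus-rhythm group holds the information needed to separate the two effects, but only if hypertension status is known within AF and an analysis uses it.

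**Working it through.** **Inputs from the documents.** Difference 4.0, SD 7.5 and 78 per group (section 2.2.5); f = 0.2177324, total 234 and power 0.8509 (Appendix, Figure 1). **Assumed:** the share p of AF participants with hypertension (30%, 50%, 70%), and the position q of the hypertensive sinus-rhythm mean as a fraction of the way from NSR to AF.

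**1. The plan's own figure.** Means 0, 2, 4 with SD 7.5 give f = √(8/3)/7.5 = 0.21773. With 234 participants, λ = 234 × f² = 11.093 and power is 0.8509. This matches the Appendix and corresponds to q = 0.5.

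**2. Share of the NSR–AF difference due to hypertension.** If hypertension acts equally in both rhythms, the share is q × p, whatever the strain scale.

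| q | p = 30% | p = 50% | p = 70% |
|---|---|---|---|
| 0.25 | 7.5% | 12.5% | 17.5% |
| 0.50 | 15% | 25% | 35% |
| 0.75 | 22.5% | 37.5% | 52.5% |

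If hypertension acts half as strongly in AF, the middle row is halved to 7.5%, 12.5% and 17.5%.

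The point values below use the contractile planning scale and are illustrations only, because section 1.1 says that phase may not be analysable in AF.

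**3. Precision of an adjusted estimate.** Take 23, 39 or 55 of 78 AF participants as hypertensive. In a linear model on rhythm and hypertension, the rhythm coefficient is a weighted average of two contrasts: AF without hypertension versus NSR, and AF with hypertension versus hypertensive NSR. Each weight is proportional to n₁n₂/(n₁+n₂).

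- 23 hypertensive: 55×78/133 = 32.26 and 23×78/101 = 17.76, so SE = 7.5/√50.02 = 1.060.
- 39 hypertensive: 26 and 26, so SE = 7.5/√52 = 1.040.
- 55 hypertensive: the mirror image of 23, so SE = 1.060.
- Unadjusted t-test: 7.5 × √(2/78) = 1.201.

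**4. Error in the AF effect.** Take a 2-point hypertension effect in sinus rhythm; a positive error overstates AF.

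| Hypertension effect in AF | Adjusted (23 / 39 / 55) | Unadjusted (23 / 39 / 55) |
|---|---|---|
| Same | 0 / 0 / 0 | +0.59 / +1.00 / +1.41 |
| Halved | −0.355 / −0.500 / −0.645 | +0.295 / +0.500 / +0.705 |
| 1.5 times | +0.355 / +0.500 / +0.645 | +0.885 / +1.500 / +2.115 |

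In the halved case the hypertensive stratum is off by −1 point, and its weight is 17.76/50.02 = 0.355 when 23 are hypertensive. Adjustment is then slightly worse at about 30% hypertension, equal in size at 50% and slightly better at 70%.

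**5. Power, two-sided 5%, noncentral t.** For an adjusted AF effect of 4.0 − 2p (3.4, 3.0, 2.6) on 231 df, power is about 0.89, 0.82 and 0.68. The unadjusted t-test at 4.0 has 0.91. A direct AF versus hypertensive-NSR contrast of 2.0 points has about 0.38. That contrast would also understate AF by 2(1−p), that is 1.4, 1.0 or 0.6 points, because not all AF participants are hypertensive.

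**The case against.** The stated hypotheses in section 2.1 and the outcomes in 2.3 ask whether strain differs between groups, and the planned tests answer that. No sentence commits to attributing the whole difference to AF. This stands, and it limits the point to interpretation and to the predictive scale.

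The plan also controls more than a quick reading suggests: age matching, the shared exclusions, and a third group included because of hypertension. This stands too, which is why that group counts as a partial safeguard. It does not remove the problem, since an omnibus three-group test does not separate rhythm from hypertension. The open-ended data list means that hypertension in AF may be recorded after all, but nothing commits to it.

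Two stronger readings are tempting, and the documents support neither.

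- A reader might infer from f that the sponsor expects a 2-point hypertension effect, half of the 4.0. But for a fixed range of means, even spacing gives the smallest f, so it may be no more than a cautious convention.
- A reader might add valve disease, because "Patients with AF that have < moderate valvular pathologies may be considered" while the plan excludes "subjects with any valvular pathologies in the control and disease-control groups". The documents do not say that lesions below moderate alter strain; section 1.1 cites aortic stenosis and valve replacement. No valve sensitivity analysis is asked for here.

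**Conclusion.** The gap is plain in the text: hypertension is absent by design from the NSR controls, unrestricted in AF and not used in any comparison. Its size is unknown, because the documents give neither the prevalence of hypertension in AF nor reservoir or conduit values. The 15% to 35% share rests on q = 0.5, p between 30% and 70% and an equal effect in both rhythms; q between 0.25 and 0.75 widens it to roughly 8% to 53%. These figures show what is possible, not what is likely. The planned tests remain valid for group difference. The change is a cheap improvement that should be made before a difference is credited to AF.

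**What to change.** Record hypertension (yes/no) for every AF participant. In section 2.2.6 keep the planned tests and prespecify beside them, for reservoir and conduit strain (LA area and volume as secondary), one linear model on rhythm, hypertension, age and sex using all three groups. Report the rhythm coefficient with its 95% CI. Show AF without hypertension versus NSR, and AF with hypertension versus hypertensive NSR, as descriptive checks. Keep any direct AF versus hypertensive-NSR contrast descriptive, given its low power. Before attributing a difference to AF, report the adjusted and unadjusted estimates together.

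The cost is one data field, one model per outcome and the descriptive checks; linear regression is already planned, and age and sex are already recorded. The limits should be stated:

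- The model assumes that hypertension acts equally in both rhythms. The descriptive checks would show a departure only imprecisely (SE 1.3 to 1.8 points each on the planning scale).
- The hypertensive group is free of valve disease and of reduced ejection fraction, but it is not required to be otherwise healthy as the NSR controls are. Its coefficient may therefore absorb other comorbidity; each 1 point of such effect would understate AF by 0.355, 0.500 or 0.645 points.
- A yes/no field does not separate controlled from uncontrolled hypertension.
- Other comorbidity in AF stays unadjusted.

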#### 2.2.3 Study Populations, Subject Selection, Recruitment and Study Schedule

Sampling design - only patients that have been referred for a transthoracic echocardiogram will be included as part of this study. Patient referrals will be screened to assess whether the patients fit into either of the three study groups. On patient arrival, patients that are deemed to be eligible thus far will be provided with an explanation of the study, patient information documents, and written informed consent is to be invited and received. Departmental sonographers may initiate Research discussion with patient either pre-during or post-scan, prior to the CI explaining the study in full and obtaining written informed consent. Providing that the transthoracic scan images are of a good enough quality to obtain strain measurements, the patient will be included as part of the study. Recruitment options will be tailored to the participant and may be either remotely or at time of clinic visit. Once potential candidates have been screened, it is envisaged that the invitation letter, Participant Information Sheet (PIS), Informed Consent Form (ICF) and a template ICF will be posted to the participant along with their appointment letter for an echocardiogram. This will allow plenty of time for potential participants to read over the PIS. The patient then may be contacted prior to their appointment via telephone to discuss the study and participant involvement and give verbal consent. If this is not feasible, the study should be discussed with patient during their appointment visit and written consent can be obtained. If the CI is not able to discuss the study with the patient at either of these times, the patient may be telephoned following their scan to discuss and provide verbal consent.

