#### 2.2.4 Eligibility Criteria

Patients must be in one of the following categories to be included: normal sinus rhythm, normal sinus rhythm with controlled hypertension and chronic atrial fibrillation (persistent or permanent). Patients with paroxysmal AF may also be included but only as part of subsequent analysis when comparing strain measurements between AF groups. Additionally, eligible patients must conform to the following inclusion and exclusion criteria.

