# 3. Screening, Consent and Withdrawal

# 3.1 Screening Duties

The Chief Investigator will be responsible for screening potential participants. This will be done by reviewing both in-patient and out-patient referrals to look for patients that are in one of the following categories: normal sinus rhythm, normal sinus rhythm with controlled hypertension and chronic atrial fibrillation. Subsequently, this can be further refined by excluding patients based on age, valvular pathologies and ventricular dysfunction.

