# 4.4 Confidentiality

For patients that wish to participate in this study, all signed Informed Consent Forms will be securely stored in the Investigator Site File within the Cardio-Respiratory Department and must not leave the department under any circumstances. The participant data will undergo pseudo-anonymisation via the use of two password-protected excel spreadsheets. One spreadsheet will contain participant numbers and corresponding hospital ID numbers. The second spreadsheet will include participant numbers along with patient demographics (i.e., sex, age, participant group, reason for patient referral, etc.). This data will be encrypted and the folder it resides in will also be encrypted and password protected. This will be stored on an NHS OneDrive account on a departmental computer. General data protection regulation (GDPR) will be maintained and followed throughout.

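### Both sinus-rhythm groups come from echo referrals that routinely include suspected AF, and neither the criteria nor the analysis plan deals with those patients

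*Combined protocol and SAP*

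**What the plan says.** **Source of participants.** Section 2.2.3 states that "only patients that have been referred for a transthoracic echocardiogram will be included as part of this study". This applies to the controls as well as the AF patients. The Introduction says "Patients suspected of having AF are routinely referred for a transthoracic echocardiogram (TTE"), and adds that "A diagnosis of AF can be incidental as not all patients are symptomatic".

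**Group definitions (2.2.4).** The control group is "Known to be in normal sinus rhythm, are normotensive and have no underlying health problems". The disease-control group is "Known to be in normal sinus rhythm and have controlled hypertension", with diagnosis and treatment of the hypertension required but no clause on other health problems. How sinus rhythm is to be known, or over what period, is not stated. Section 2.2.2 provides for one visit, at which rhythm is recorded.

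**AF already recognised.** Section 2.2.4 says "Patients with paroxysmal AF may also be included but only as part of subsequent analysis when comparing strain measurements between AF groups". Section 2.2.5 also describes the hypertensive comparators as free of AF.

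**Suspected AF.** No inclusion or exclusion criterion mentions AF history, suspected AF or referral reason. On screening, section 3.1 says "this can be further refined by excluding patients based on age, valvular pathologies and ventricular dysfunction". Section 4.4 lists "reason for patient referral" among the recorded items, but section 2.2.6 makes no use of it.

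**The concern.** A patient sent for an echo because AF is suspected, and in sinus rhythm on the day, can meet the hypertensive definition outright. That patient can arguably meet the control definition too, since an unconfirmed suspicion is not a diagnosed health problem. If some of these patients have unrecognised paroxysmal AF, two things follow.

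- The NSR mean moves towards the AF mean, so the main difference is understated.
- The plan expects hypertensive strain to lie between the other two groups. An intermediate value could then reflect hypertension, hidden AF, or both, and the planned analyses could not tell these apart. The same blur would carry into the predictive scale that the Introduction wants to build from these groups.

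**Working it through.** **Inputs.** Section 2.2.5 gives an NSR–AF difference of 4.0, SD 7.5, 78 per group, alpha 0.05 and power 0.85. The appendix gives f = 0.2177324, noncentrality 11.0933 and power 0.8509. The share q of unrecognised AF is not in the documents, so 5%, 10% and 20% are assumptions.

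**1. Reproduce the plan's figure.** Measure means from the AF group: AF 0, hypertensive 2, NSR 4. The midway hypertensive value is not stated, but it is what reproduces the appendix.

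- f = √(8/3) / 7.5 = 0.2177
- λ = 78 × (4 + 0 + 4) / 56.25 = 11.0933
- Critical F(2, 231) = 3.0349, power 0.8509, total 234. This matches.

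**2. NSR–AF t-test, no contamination.** Noncentrality = (4.0/7.5) × √(78/2) = 3.331 on 154 df; two-sided power 0.911.

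**3. Full shift in both sinus-rhythm groups.** If a share q has AF-like strain, the means become 4(1 − q), 2(1 − q) and 0, so λ is multiplied by (1 − q)².

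| q | NSR–AF difference | λ | Omnibus power | t-test power |
|---|---|---|---|---|
| 0 | 4.0 | 11.09 | 0.851 | 0.911 |
| 5% | 3.8 | 10.01 | 0.811 | 0.882 |
| 10% | 3.6 | 8.99 | 0.764 | 0.846 |
| 20% | 3.2 | 7.10 | 0.656 | 0.754 |

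The SD is held at 7.5. Mixing adds a little spread: at 20% the NSR SD becomes √(56.25 + 0.2 × 0.8 × 16) = 7.67, which lowers t-test power by a further 0.01 or so.

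**4. Half shift.** If hidden cases move only halfway to AF values, the multiplier is (1 − q/2). Omnibus power is 0.832, 0.811 and 0.764; t-test power is 0.897, 0.882 and 0.846.

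**5. Which group matters for what.** With a full shift in the NSR group alone, omnibus power is 0.811, 0.766 and 0.666, almost the same as in step 3. With a full shift in the hypertensive group alone it stays at 0.851 to 0.856. The power loss therefore comes from the NSR group, and in the hypertensive group the problem is one of interpretation. If hypertension itself had no effect, hidden AF in a share q of that group would lower its mean by 4q, that is 0.2, 0.4 or 0.8, against the 2.0 implied by the midway assumption.

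**The case against.** The other side has several fair points, and most of them stand.

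- **Existing text does part of the work.** Recognised AF and paroxysmal AF are already outside both sinus-rhythm groups, and the control group's good-health clause may remove some suspected cases. What remains is unrecognised AF, with the clearest gap in the hypertensive group.
- **No rate is available.** A reader might infer that AF often goes undetected, or that a healthy person over 50 sent for an echo is probably under investigation for arrhythmia. The documents say only that AF can be silent and that suspected AF leads to an echo. They give no breakdown of referral reasons and no yield of AF among suspected cases.
- **Full AF-like strain is extreme.** The power inputs concern contractile strain. The Introduction and section 1.1 say this is absent in AF because the atrium does not contract normally. A contaminating control is in sinus rhythm during the scan, so the full shift is close to a ceiling for each fraction.
- **The NSR–AF test has some margin.** It stays near 85% with 10% fully shifted or 20% half shifted.
- **Exclusion is not clearly better.** Removing suspected-AF patients from the comparators could leave unusually healthy controls and exaggerate the separation. It would also drop people relevant to the early-prediction question in section 1.2.

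These points limit the size of the problem and argue against an eligibility change as the first remedy. They do not explain why a recorded referral reason should go unused.

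**Conclusion.** The gap is real but of unknown size. Patients referred for suspected AF can enter either sinus-rhythm group, and nothing planned would show whether they influence the result. The direction is towards a smaller NSR–AF difference and a less interpretable hypertensive value.

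The power figures illustrate sensitivity and do not forecast a loss. They rest on assumed fractions, evenly spaced means, a common SD of 7.5, and a strain component that section 1.1 says may not be analysable in AF.

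Two stronger readings are not supported. One is that the sample size is wrong: it reproduces exactly on its own inputs. The other is that hidden AF alone would explain an intermediate hypertensive result. On the plan's figures, with an AF-free NSR group and no effect of hypertension, a full 2.0 shift would need 4q = 2, so half of that group would have to have fully AF-like strain.

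**What to change.** In section 2.2.6, pre-specify a repeat of the NSR–AF and three-group comparisons that leaves out NSR and hypertensive participants whose recorded referral reason is suspected AF, palpitations or another suspected arrhythmia. Use the same test as in the main analysis, and report the repeat beside the main result with the number left out of each group. Code the referral reason into these categories before the strain values are compared.

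**Cost.** No extra recruitment, visits or data items; the work is one coding step and one repeated analysis.

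**Limits.** Precision falls in the subset. With the plan's SD, the standard error of the NSR–AF difference is 7.5 × √(2/78) = 1.20. It becomes 7.5 × √(1/62 + 1/78) = 1.28 if 16 of the 78 controls are left out, and 7.5 × √(1/39 + 1/78) = 1.47 if half are. These numbers left out are assumptions. The repeat should therefore be read on the estimated difference and its interval, not on whether significance is kept. It also cannot remove asymptomatic AF that the referral does not mention.

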# 1.1 Background

From the current literature available (*see document Literature Review Table*), it has been suggested that there is a correlation between AF and LA strain values. Existing literature suggests that patients in AF have a reduced LA strain value compared to patients in NSR. However, there are limited studies which also include controlled hypertensive patients despite collecting data regarding blood pressure. Furthermore, the majority of literature reviewed appears to focus on patients that have other comorbidities, and it could be argued that these can affect the parameters measured and analysed. This includes studies involving patients with valvular pathologies such as aortic stenosis and aortic valve replacements as well as studies involving patients with potential structural heart deformations such as those seen with heart failure or following a myocardial infarction. These factors may alter strain patterns and LA size as a result. By listing these factors as exclusion criteria, this study should minimise any external and uncontrollable factors which may affect LA strain value and LA size.

Furthermore, some studies do not have a standardised zero-reference point as some studies used the P wave for NSR and the R wave for AF patients which may cause a discrepancy in results. In this study, it has been agreed that the zero-reference point will be the R wave to create R-R cycles. This is because the P wave is not present in AF and thus cannot be used as a definitive reference point within the AF group. Both groups will have R waves present and therefore, the reference-point can be standardised across all three groups. Additionally, many of the studies reviewed appear to focus on only one LA strain and phase within the cardiac cycle. However, some do include all three. This study will include all three strain values as well as peak atrial longitudinal strain (PALS) values. However, statistical analysis may not be doable for the contractile phase as this is not present in patients with AF. The biggest pitfall that is common to most, if not all, studies reviewed is that the methods used to calculate LA strain were originally designed to measure global longitudinal strain (GLS) of the left ventricle (LV). This study utilises the automated function imaging (AFI) LA atrial strain tool provided by GE Healthcare which is specific to the LA as opposed to GLS methods to track the LV.

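### Only the sinus-rhythm controls must be free of other health problems, so both the hypertension and the AF contrasts with control mix the group condition with any comorbidity not otherwise excluded

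*Combined protocol and SAP*

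**What the plan says.** Section 2.2.4 defines three groups. Controls are in sinus rhythm and "are normotensive and have no underlying health problems". The disease-control entry reads "Known to be in normal sinus rhythm and have controlled hypertension", with a professional diagnosis and appropriate medication. The AF entry asks for diagnosed persistent or permanent AF with appropriate anticoagulation. Neither of these two entries limits other disease.

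Some comorbidity is removed by other rules. The exclusion list drops "subjects with any valvular pathologies in the control and disease-control groups", at-least-moderate valve disease in AF, and, in every group, EF below 50%, permanent pacing and previous cardiac surgery. The only matching is that "subjects will be age matched across all three groups".

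Section 1 explains that the hypertensive group is there because hypertension can itself remodel the atrium, and it expects this group's strain to lie between NSR and AF. Section 1.1 faults earlier work for studying "patients that have other comorbidities, and it could be argued that these can affect the parameters measured and analysed". Sections 2.1 and 2.3 make the three-group comparison an aim and a key outcome.

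Section 2.2.6 plans a t-test of NSR against AF and a one-way ANOVA across the three groups, or rank equivalents, with no covariates. The data lists in sections 2.2.2 and 4.4 do not name comorbidity.

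**The concern.** The control group is screened on general health and the other two groups are not. The groups therefore differ by selection on two things at once: the condition that defines the group, and every other condition that the exclusion list leaves in. Obesity and alcohol, which section 1 names as AF risk factors, are not excluded from the hypertensive or AF groups. Nor are heart failure with EF of 50% or more, or a past infarction without surgery. Section 1.1 names heart failure and infarction among the factors that may alter strain and says that exclusion criteria will handle such factors, but the exclusion list names neither.

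An intermediate strain value in the hypertensive group would match the expectation in section 1 even if hypertension itself contributed nothing. The same reasoning applies to the NSR-AF difference, which is the comparison in the hypotheses of section 2.1 and the basis of the sample size. If comorbidity is not recorded, the question cannot be examined at analysis.

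**Working it through.** **1. Does any other rule close the gap?**

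| Safeguard | Where | Closes it? |
|---|---|---|
| Valve, EF, pacing and surgery exclusions | 2.2.4 | In part; other conditions remain, and mild valve disease is allowed in AF only |
| Matching | 2.2.4 | No; age only |
| Adjustment | 2.2.6 | No covariate in the group comparisons |
| Recorded data | 2.2.2, 4.4 | Comorbidity not named, though the list in 4.4 is open-ended |

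**2. Reproduce the plan's figure.** Inputs from section 2.2.5 and Appendix Figure 1: difference 4.0, SD 7.5, alpha 0.05, power 0.85, three groups, f = 0.2177324.

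With group means 0, 2 and 4, the standard deviation of the means is √[((−2)² + 0² + 2²)/3] = √(8/3) = 1.633, and f = 1.633/7.5 = 0.2177. With N = 234, λ = f² × N = 11.093, the critical F is 3.0349 and power is 0.8509. All of these match the output.

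With a range of 4.0 and SD 7.5, this f arises only when the middle group sits midway. If the hypertensive group is the middle one, as section 1 expects, the implied hypertensive-NSR gap is 2.0 points.

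**3. Illustrate the bias.** The documents give neither input, so both are assumptions. Set the true hypertension effect to zero. Then

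spurious difference = excess prevalence of the other condition × its effect on strain.

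| Excess prevalence | Effect (points) | Spurious difference | Share of 2.0 |
|---|---|---|---|
| 20% | 2 | 0.4 | 20% |
| 50% | 2 | 1.0 | 50% |
| 50% | 4 | 2.0 | 100% |
| 50% | 6 | 3.0 | 150% |

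If the AF group had the same 50% excess and 2-point effect, 1.0 of the assumed 4.0-point NSR-AF difference (a quarter) would be comorbidity.

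**4. Precision of a restricted analysis.** The assumption is that half of the 78 hypertensive participants (39) have no other health problem.

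- Full comparison: SE = 7.5 × √(1/78 + 1/78) = 1.20. Two-sided 5% t-test power for 2.0 points is 38%.
- Restricted: SE = 7.5 × √(1/78 + 1/39) = 1.47. Power for 2.0 points is about 27%.

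**The case against.** **Some comorbidity is already excluded.** This stands. The confounding is with what remains after the exclusions, not with all other disease.

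**The group can still do part of its job.** A reader might infer that the disease-control group is useless. The documents do not support that. Section 1 states an expectation about where its strain will lie, and the study can describe that. The hypotheses in section 2.1 concern NSR and AF only, and nothing commits the authors to attributing a difference to hypertension alone. What is lost is attribution.

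**False-positive rates.** A reader might convert the 1.0-point shift into an inflated error rate: a two-sample t-test at 78 per group would reject 13% of the time instead of 5%. Section 2.2.6 names no hypertensive-NSR pairwise test. In the ANOVA that it does plan, with a true 4.0-point NSR-AF difference, rejection is 94% when the hypertensive mean equals NSR and 88% when it is shifted by 1.0, so the omnibus test shows no such inflation there. The 13% is not a property of the plan.

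**The benchmark is indirect.** The 2.0-point gap is back-calculated, not stated. The midpoint is also the configuration that gives the smallest f for a fixed range, so it may be only a cautious sizing choice. The calculation concerns contractile strain, which the protocol expects to be absent in AF. The 2.0 is therefore a yardstick and no more.

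**Comorbidity may be collected anyway.** The list in section 4.4 is open-ended, and health problems must be checked to classify controls. So comorbidity is unnamed, not shown to be uncollected. But nothing requires it in the other groups or uses it in an analysis.

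**Conclusion.** The concern holds in a limited form. The difference in eligibility is explicit, and neither matching, analysis nor the listed data corrects it. Differences from NSR in the hypertensive and AF groups will mix the defining condition with comorbidity that is not otherwise excluded. This conflicts with the study's own criticism of earlier work in section 1.1. It limits interpretation; it does not invalidate the study, and the sample-size calculation reproduces.

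The documents do not give the size of the bias. The 1.0-point illustration rests on an assumed 50% excess prevalence, an assumed 2-point effect and no true hypertension effect. The range shown, 0.4 to 3.0 points, runs from minor to larger than the implied gap. The structural point does not depend on these inputs.

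**What to change.** 1. In sections 2.2.2 and 4.4, name other diagnosed conditions as a recorded item for every participant in all groups.
2. In section 2.2.6, add a sensitivity analysis that repeats the group comparisons using only hypertensive and AF participants with no other health problem, judged by the standard used to admit controls.
3. Describe the full-group contrasts as hypertension, or AF, with accompanying comorbidity.

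The cost is one field, taken from the referral or record, and one extra analysis. The protocol change may need to go through the approvals in section 4.2. Eligibility and sample size stay the same.

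The main downside is precision. If half of the hypertensive group qualify, the restricted comparison has SE 1.47 instead of 1.20 and about 27% power for 2.0 points instead of 38%. It should therefore be reported as an estimate with a confidence interval, and a non-significant result should not be read as evidence that the full-group difference was confounded.
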